7.4.1.2 Methods of Recording and Assessing Adverse Events

Complete, accurate and consistent data on all SAEs and AEs of interest (serious or non-serious, related or unrelated to previous r-hGH treatment) experienced at any time during the reporting period (defined in section 7.4.1.3) will be documented by the Investigator in the appropriate section of the eCRF. All serious AEs must be additionally documented and reported using an SAE Report Form as described in section 7.4.1.4.

The CRO, PPD , will check legibility, consistency and plausibility of all AE reports and will forward all these reports to the Sponsor (Merck KGaA) within 24 hours. Furthermore, PPD will serve as an interface between the Sponsor and the site/Investigators, and will ensure that queries and follow-up information are managed accordingly.

It is important that each AE report (in the eCRF/SAE Report Form) includes a description of the event, its duration (onset/start and resolution/end dates), its severity, its relationship with the previous r-hGH treatment, any other potential causal factors, any treatment given or other action taken, and its outcome. In addition, serious cases should be identified and the appropriate seriousness criteria documented.

Specific guidance can be found in the eCRF Completion and Monitoring Conventions provided by the Sponsor.

7.4.1.3 Definition of the Adverse Event Reporting Period

The AE reporting period for safety surveillance is defined as the 10-year period after cessation of r-hGH treatment (i.e., during the 10 years after the date of last r-hGH administration).

7.4.1.4 Procedure for Reporting Serious Adverse Events

In the event of any new SAE related to the previous r-hGH treatment or any SAE of interest (related and not related) occurring during the reporting period, the Investigator must immediately (i.e. within a maximum **24 HOURS** after becoming aware of the event) inform the CRO, PPD, by phone, fax or by email. Non-serious AEs of interest (related and not related) are sent to the CRO within one week. The reports have to be sent by phone, fax or by email to the contact details below:

Email: PPD

Fax: PPD

Safety Hotline: PPD

The CRO, PPD , will check legibility, consistency and plausibility of all AE reports and will forward all these AE reports to the Sponsor (Merck KGaA) within 24 hours. Furthermore, PPD will serve as an interface between the Sponsor and the site/Investigators, and will ensure that queries and follow-up information are managed accordingly.

When an event (or follow-up information) is reported by telephone, a written report must be sent immediately thereafter by fax or email, in the format of a SAE Report Form.

Reporting procedures and timelines are the same for any new information on a previously reported SAE related to r-hGH treatment or SAE of interest (= follow-up).

For names, addresses, telephone and fax numbers for SAE reporting, see information included in the SAE Report Form or the protocol, or as applicable, in a specific document including Sponsor contact details.

All written reports on SAEs should be transmitted using the SAE Report Form, which must be completed by the Investigator following specific completion instructions. Relevant pages from the eCRF may be provided in parallel (e.g., medical history, concomitant drugs). In all cases, the information provided in the SAE Report Form must be consistent with the data on the event that are recorded in the corresponding sections of the eCRF.

The Investigator must respond to any request for follow-up information (e.g. additional information, outcome and final evaluation, specific records where needed) or to any question the Sponsor may have on the AE of interest within the same timelines as described for initial reports. This is necessary to permit a prompt assessment of the event by the Sponsor and (as applicable) to allow the Company to meet strict regulatory timelines associated with expedited safety reporting obligations.

Requests for follow-up will usually be made by the responsible Merck KGaA personnel, although in exceptional circumstances the Global Patient Safety department may contact the treating physician directly to obtain clarification or to discuss a particularly critical event.

7.4.1.5 Safety Reporting to Regulatory Authorities, Investigators and Ethics Committees

The Sponsor will send appropriate safety notifications to regulatory authorities in accordance with applicable laws and regulations.

The Investigator must comply with any applicable specific requirements related to the reporting of SAEs involving his/her subjects to the Ethics Committee (EC) that approved the study.

The Sponsor will inform the Investigator or general practitioner of findings that could adversely affect the safety of subjects in accordance with applicable laws and regulations.

The Investigator should place copies of safety reports in the Investigator Site File. National regulations with regard to Safety report notifications to Investigators will be taken into account.

When specifically required by regulations and guidelines, the Sponsor will provide appropriate Safety reports directly to the concerned lead EC and will maintain records of these notifications. When direct reporting by the Sponsor is not clearly defined by national or site-specific regulations, the Investigator will be responsible for promptly notifying the concerned EC of any Safety reports provided by the Sponsor and of filing copies of all related correspondence in the Investigator Site File.

7.4.1.6 Monitoring of Subjects with Adverse Events

Type 2 diabetes mellitus, metabolic syndrome and/or changes in glucose metabolism parameters (glycaemia parameters- fasting blood glucose and postprandial glucose, fasting insulin levels, HbA_{1c}, 2-hour OGTT results, blood pressure, lipid parameters) and any malignancy that occurs during the course of the study and any SAE that is considered to be probably or possibly related to previous r-hGH treatment. Correlation of type 2 diabetes mellitus and/or malignancy will be established against blood pressure, body mass index, lipid parameters, medical history and familial inheritance.

Safety reports submitted to Global Patient Safety (related SAEs, AEs and SAEs of interest) will be followed up. Reasonable attempts to obtain this information must be made and documented. It is the responsibility of the subject's medical care provider to ensure that any necessary additional therapeutic measures and follow-up procedures are performed.

7.4.2 Pregnancy and In Utero Drug Exposure

Not applicable. Subjects are not exposed to drug during this observational study. Nevertheless, any SAE in a pregnant women or the newborn assessed as related to the previously received r-hGH treatment should be reported as described in section 7.4.1.4.

7.4.3 Laboratory Assessments

No scheduled laboratory assessments are required by protocol. Nevertheless, laboratory data of interest related to glucose metabolism, metabolic syndrome or any malignancy (see Table 1)

deemed necessary and requested by the treating physician/GP as part of the subject's standard medical care, will be, when available, recorded into the eCRF by the Investigator (see section 7.1).

7.4.4 Vital Signs, Physical Examinations, and Other Assessments

Blood pressure, height, weight and waist circumference will be collected when available.

7.5 Pharmacokinetics

Not applicable.

7.6 Biomarkers/Pharmacogenetics (PGX)

Not applicable.

7.7 Other Assessments

Not applicable.

8 Statistics

[figure not shown]
8.1 Sample Size

It has been agreed with the Health Authorities to organize an observational study to have followup data on a minimum of 200 subjects born SGA for 10 years after cessation of Saizen® or other r-hGH therapies.

It has been estimated that up to 35% of subjects are likely to be lost or will drop out during the 10-year study duration (which can be due to withdrawal of consent, lost to follow-up, or death). Therefore, it was decided to recruit approximately 300 subjects in the SALTO study to have the 200 subjects for the final analysis at 10 years of follow-up. The sample size of 300 subjects represents 150% of the 200 subjects completing the study, as requested by the Health Authorities.

While recruitment is still open, the Sponsor will closely monitor the subject dropout rate to determine the need to recruit additional subjects. If the attrition rate is anticipated to be greater than 35%, additional subjects may be recruited to maximize the probability that 200 patients will have completed the study.

Figure 2 Determination of planned sample size.

^{*}Discontinuation includes: Lost to FU, protocol deviation, non-compliance, AEs, patient decision and other reasons.

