	 Exclusion criteria Patients unwilling and/or parents/guardians who are not capable of ensuring compliance with the study protocol. Patients enrolled in an interventional trial Patients enrolled in an observational trial of a similar nature to the SALTO study, where the protocol includes reporting of incidence of type 2 diabetes mellitus and/or malignancies after cessation of r-hGH therapy. 		
Investigational Medicinal Product (s): dose/mode of administration/dosing schedule	Not Applicable (observational study).		
Reference therapy(ies): dose/mode of administration/ dosing schedule	None (post-treatment observational study).		
Planned treatment duration per subject	None (post-treatment observational study).		
Primary endpoint(s)	Incidence of type 2 diabetes mellitus		
	Incidence of any malignancy		
Secondary endpoint(s)	• Incidence of metabolic syndrome and changes in glucose metabolism parameters (glycaemia parameters – fasting plasma glucose and postprandial glucose, fasting plasma insulin levels, HbA1c, 2-hour oral glucose tolerance test (OGTT) results, blood pressure, lipid parameters).		
	 Parameters related to malignancies (typology, size and location as applicable, grading, severity, treatment, outcome) 		
	Correlation of type 2 diabetes mellitus and/or malignancy will be established against blood pressure, body mass index, lipid parameters, medical history and familial inheritance		
Statistical methods (includes sample size calculation)	It has been agreed with the Health Authorities to organize an observational study to follow-up 200 short children born SGA for 10 years after cessation of treatment with Saizen® or other r-hGH products. In order to compensate for an estimated 35% loss to follow-up, we will recruit 150% of the requested target number of 200 subjects. Hence, a sample size of approximately 300 subjects is targeted for study enrolment.		

Numbers and proportions of subjects having the events (type 2 diabetes mellitus and any malignancy), will be computed, as will the incidence rate per subject-years of follow-up during the 10-year follow-up. Analysis of correlations of the primary endpoints with subject characteristics (e.g., age, blood pressure, Body Mass Index [BMI], family history) and possible confounding factors of the diseases (e.g., concomitant treatment, environmental factors) will be conducted. Exploratory analysis will be performed for each brand of r-hGH product if permitted by sample size per brand.

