2. Malignancy risk: low birth weight has not been shown to be associated with increased risk of cancer in general, with the possible exceptions of testicular and renal cancer (4). A number of studies were retrieved in the published literature discussing the occurrence and/or recurrence of cancer or neoplasm during GH therapy. In one medium-sized and two large studies, GH therapy was not associated with an increase in the incidence of a first cancer compared to the general population.

However, GH treatment during childhood of survivors of cancer treatment has also been shown to increase slightly the relative risk of a second neoplasm (15), (16). Growth hormone therapy studied in two populations of cancer survivors, one with a control group, found an elevated risk of developing a secondary solid tumour in childhood cancer survivors treated with GH compared with non-treated survivors for one and a statistically significant raised frequency of colon cancer mortality after pituitary-derived GH treatment in another.

This observation is however disputed, given that other surveillance studies revealed no increase in observed cancer risk (17). The above results are based on a very small number of cases and may therefore require cautious interpretation.

There have been rare reports of brain tumours (de novo/recurrence) or leukaemia and extra-cranial solid tumour in subjects treated with Saizen® in the post-marketing surveillance period. From the currently available data, there is no evidence suggesting that Saizen® may increase the risk of cancers in treated subjects. It must also be noted that with an overall increase in subject-years of exposure, adverse events (AEs) which are related to commonly experienced medical conditions (as seen in the general population) tend to also be reported in the population treated with GH. However, no increase of reporting rates concerning neoplasms, both de novo and recurrence, was identified cumulatively since first marketing authorization of Saizen®.

4 Study Objectives

Primary objective of the study:

To assess the long-term safety of Saizen® or other r-hGH treatment for 10 years after cessation
of treatment, in terms of occurrence of type 2 diabetes mellitus and malignancies, in a minimum
of 200 subjects born SGA who received Saizen® or other r-hGH products for the treatment of
short stature

Secondary objectives of the study:

- To assess occurrence of metabolic syndrome
- To assess glucose metabolism parameters

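### Enrolling 150% of 200 subjects offsets a 33.3% loss, not the stated 35%, and the top-up threshold of more than 35% sits slightly too high for the 200-completer minimum

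*Protocol*

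**What the plan says.** Section 8.1 of the protocol gives the target agreed with the Health Authorities as follow-up data on "a minimum of 200 subjects born SGA for 10 years after cessation" of treatment. The primary objective (section 4 and synopsis) also calls 200 a minimum.

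For attrition, section 8.1 expects that "up to 35% of subjects are likely to be lost or will drop out during the 10-year study duration", and counts withdrawal of consent, loss to follow-up and death. The synopsis (statistical methods) drops the qualifier and gives a plain estimate: "In order to compensate for an estimated 35% loss to follow-up, we will recruit 150% of the requested target number of 200 subjects".

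For enrolment, section 8.1 says "it was decided to recruit approximately 300 subjects in the SALTO study to have the 200 subjects for the final analysis" at 10 years, and explains the number thus: "The sample size of 300 subjects represents 150% of the 200 subjects completing the study, as requested by the Health Authorities".

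For corrective action, section 8.1 first commits the sponsor to watch the dropout rate while recruitment is open and to judge whether more subjects are needed. It names no threshold there. It then gives one numerical criterion: "If the attrition rate is anticipated to be greater than 35%, additional subjects may be recruited". The stated purpose of that step is to make it as likely as possible that 200 subjects complete. Under section 5.3.4.1, withdrawn subjects are not replaced.

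**The concern.** The enrolment figure and the attrition figure are presented as a matched pair, with 150% recruitment said to compensate for 35% loss. An inflation factor of 1.5 matches a loss of one third, so the pair is slightly mismatched and the expected number of completers at 35% falls below a number called a minimum.

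The same 35% is then used as the threshold for considering extra recruitment. That threshold should sit where 300 enrolled stop yielding an expected 200. It sits a little beyond that point, so there is a narrow band of attrition in which the projection is under 200 and the numerical criterion is not met.

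What is at stake is the agreed count. The 200 completers are the only basis for the sample size. The remedy is also limited in time: extra recruitment is foreseen only while enrolment is open, the last subject is expected in by 2020, and follow-up runs to 2030. A threshold that is to protect the count has to be set correctly during recruitment.

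**Working it through.** **Inputs**

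- Target completers at 10 years: 200, a minimum (section 8.1; section 4).
- Attrition over 10 years: up to 35% (section 8.1); 35% (synopsis).
- Planned enrolment: approximately 300, described as 150% of 200 (section 8.1; synopsis).
- Numerical top-up threshold: anticipated attrition greater than 35% (section 8.1).

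**1. The plan's own figure.** 1.5 × 200 = 300. The 150% rule reproduces exactly.

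**2. Loss that 300 enrolled can absorb.** 1 − 200/300 = 0.333, so 33.3%, or 100 subjects of 300.

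**3. Expected completers at the stated loss.** 300 × (1 − 0.35) = 195. Shortfall: 200 − 195 = 5, and 5/200 = 2.5%.

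**4. Enrolment that matches 35% loss.** 200/(1 − 0.35) = 307.7, rounded up to 308. Against 300 the gap is 8 subjects, and 8/300 = 2.7%.

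**5. Where the threshold sits.** Expected completers from 300 enrolled are 300 × (1 − loss). The last column is the binomial chance of at least 200 completers. It assumes that subjects drop out independently with the same probability, which the protocol does not state.

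| Loss | Expected completers | Threshold met? | Chance of at least 200 |
|---|---|---|---|
| 30% | 210 | no | 0.91 |
| 32% | 204 | no | 0.71 |
| 33.3% | 200 | no | 0.53 |
| 34% | 198 | no | 0.43 |
| 35% | 195 | no | 0.29 |
| 36% | 192 | yes | 0.18 |

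The break-even is 33.3% and the threshold is 35%, a gap of 35 − 33.3 = 1.7 percentage points. Within that gap, 195 to 200 completers are expected and the numerical criterion is not met.

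**6. Check of the alternative enrolment.** 308 × 0.65 = 200.2 expected completers at 35% loss. Under the same binomial assumption the chance of at least 200 is 0.54. So 308 matches the target on average, as 300 does at 33.3%. Neither makes 200 highly likely.

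**The case against.** The strongest reply is that this is rounding. Enrolment is approximate throughout the protocol, and 308 differs from 300 by 2.7%. That stands: a reader might infer that the sample size was miscalculated, or that the target, the attrition rate and the enrolment figure cannot be held together. The text does not support either inference, because nothing fixes enrolment at exactly 300, and section 8.1 gives 35% as an upper bound, so 195 is the worst case within that assumption. The plain 35% in the synopsis keeps the mismatch alive but does not enlarge it.

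A reader might also infer that the plan would let the target be missed without any action. That goes too far. The sentence before the 35% criterion commits the sponsor to monitor dropout and judge the need for more subjects, with no threshold attached. Adding subjects at 34% projected loss is therefore open to the sponsor, and the 35% sentence is itself permissive. What remains is that the only number offered to guide that judgement is not the number at which 200 is lost.

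The consequence is small. No significance testing is planned (section 8.5.1), the safety population is all included subjects and not only completers (section 8.4), and incidence rates per subject-years are also planned (section 8.5.2). With no events, the one-sided 95% upper limit for a proportion, 1 − 0.05^(1/n), would be 1.49% with n = 200 and 1.52% with n = 195. The 1.7-point gap is also less than one binomial standard error of a 35% proportion in 300 subjects, √(0.35 × 0.65/300) = 2.75 points, so moving the threshold would seldom change a decision. These points stand, and they keep the matter minor. They do not make the threshold consistent with its stated purpose.

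Finally, section 3 speaks of about 200 subjects and the synopsis of a target of 200, which is looser than a minimum. Section 8.1 and the primary objective nevertheless say minimum, so the plan should be consistent with that.

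**Conclusion.** A minor inconsistency, present in section 8.1 and in the synopsis. The 150% rule covers a loss of 33.3%. At 35% loss, 300 enrolled give an expected 195 completers, about 5 (2.5%) below the agreed minimum. Approximately 300 is close to the 308 that 35% loss would need, but slightly short. The numerical top-up threshold is 1.7 percentage points above the break-even.

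The effect is confined to meeting the agreed count of 200; no test or power is affected. The expected counts rest only on the protocol's figures with 300 taken as the enrolment, while the probabilities also need independent dropout. Figure 2, on how the sample size was determined, is not available in the text reviewed and could not be checked; the mismatch lies in the wording itself.

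**What to change.** Two wording changes, applicable while recruitment is open:

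1. In section 8.1, express the top-up criterion in terms of the quantity it protects: additional subjects may be recruited if projected 10-year completers fall below 200, which with 300 enrolled means attrition above about 33%.
2. In the synopsis and section 8.1, state that 300 enrolled covers a loss of up to about 33%, and that about 308 would be needed to cover 35%.

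The second change describes what 300 subjects can absorb. It should not be made by relabelling the attrition estimate itself as 33%, which would need a basis. Nor would it help simply to record that about 195 completers are expected, since that leaves the text short of its own minimum.

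The cost is an edit in two places. Top-up recruitment may be considered slightly earlier than under the present wording. No extra subjects are needed up front.

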8.2 Randomization

This is an observational study, therefore randomization is not applicable.

8.3 Endpoints

8.3.1 Primary Endpoints

The number and proportion of subjects diagnosed at any time during the 10-year follow-up will be tabulated for the two primary endpoints:

- Type 2 diabetes mellitus
- Any malignancy

8.3.2 Secondary Endpoints

- Metabolic syndrome and/or changes in glucose metabolism parameters as per
 - Glycaemia parameters, fasting plasma glucose and postprandial glucose, and/or fasting plasma insulin levels
 - HbA1c
 - 2-hour OGTT results
 - Blood pressure
 - Lipid parameters.
- Malignancies (including typology, size and location, as applicable, grading, severity, treatment, outcome)
- Correlation of type 2 diabetes mellitus and/or malignancies will be established against

- Blood pressure (BP)
- Body Mass Index (BMI)
- Lipid parameters
- Medical history
- · Familial inheritance

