- To characterize the observed malignancies
- To correlate the occurrence of metabolic syndrome and/or glucose metabolism disorders or malignancy to familial inheritance
- To correlate the occurrence of metabolic syndrome and glucose metabolism disorders or malignancy to subject characteristics and medical history.

5 Investigational Plan

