However, clinical data will be collected by the Investigator on an ongoing basis and when available during the course of this study through the subject's treating physician/GP or when provided directly by the subject/person of contact (see sections 7.1; 9.1; 9.2; 10.1). Additionally, the investigator will contact the subjects at roughly 5 and 10 years after discontinuation of r-hGH treatment in order to obtain any additional available relevant medical information (see section 7.1).

In order to minimize the subject loss during the 10 years of the follow-up study, the CRO's dedicated PMC will contact the subjects once a year to update/confirm subjects' and treating physicians' contact information in order to send them the "Yearly Subject and Investigator SALTO kits", and to identify any change in health status/medical history. If any relevant change is identified by the PMC, the PMC will notify the investigator, who will gather the relevant information from the treating physician/GP (see section 7.1).

The 5-year interim data and 10-year post-treatment data will be analysed (see section 8.6). If possible, correlation of type 2 diabetes mellitus and/or malignancy will be assessed against blood pressure, body mass index, lipid parameters, medical history and familial inheritance studies (see section 8.5).

Thus, it is anticipated that most subjects will participate in the present study between 2020 and 2030 (see Figure 1). First patient in in 2011, last patient in by 2020, and last patient out by end of 2030.

Figure 1 Study Design

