8.5.2 Analysis of Primary Safety Endpoints

For primary endpoints, details for each subject of the safety population will be listed and will include at least; time on follow-up, onset date(s) of event(s) and description of event(s).

In parallel with numbers and proportions of subjects experiencing the events, the incidence rate per subject-years of follow-up will be calculated during the 10-year follow-up. The subject-time of follow-up will be defined as the time between the day of last r-hGH treatment and the end of the 10-year period. Furthermore, an analysis of association of the primary endpoints with subject characteristics (e.g., age, sex, blood pressure, BMI, family history) and possible confounding factors of the diseases (e.g., concomitant treatment, medical history, environmental factors) will be conducted. Exploratory analysis will be performed by each brand of r-hGH product if permitted by sample size per brand.

Further details will be provided in the SAP.

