8.5.3 Analysis of Secondary Safety Endpoint(s)

All secondary endpoints will be analysed using appropriate statistics. For quantitative variables, statistics are the number of non-missing values (N), number of missing values, mean, standard deviation (SD), minimum (Min), first quartile (Q1), median, third quartile (Q3) and maximum (Max). For qualitative variables, statistics within categories are number of non-missing values (N), number of missing values and percentages of subjects.

Further details will be provided in the SAP.

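### Two secondary objectives ask how metabolic syndrome and glucose disorders relate to family history and subject characteristics, but the planned correlations cover only type 2 diabetes and malignancy

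*Protocol*

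**What the plan says.** The protocol lists five secondary objectives, in the synopsis and again in section 4. Two of them are about correlation. The first is "To correlate the occurrence of metabolic syndrome and/or glucose metabolism disorders or malignancy to familial inheritance". The second names the same outcomes and sets them against the subjects' own characteristics and their past medical history.

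The matching endpoint in section 8.3.2 reads "Correlation of type 2 diabetes mellitus and/or malignancies will be established against", followed by blood pressure, BMI, lipid parameters, medical history and familial inheritance. The synopsis and section 7.4.1.6 say the same: "Correlation of type 2 diabetes mellitus and/or malignancy will be established against blood pressure, body mass index, lipid parameters, medical history and familial inheritance". Section 5.1 repeats the restriction, subject to feasibility.

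On analysis, section 8.5.2 plans "an analysis of association of the primary endpoints with subject characteristics" and with possible confounders. Section 8.3.1 defines the primary endpoints as type 2 diabetes and any malignancy. For the rest, section 8.5.3 says "All secondary endpoints will be analysed using appropriate statistics" and then lists them: counts, missing values, mean, SD, quartiles and range for quantitative variables, and counts and percentages for qualitative ones.

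**The concern.** The objectives and the analyses name different outcomes. Metabolic syndrome comes first in both correlation objectives, yet it is not an outcome in any correlation or association the protocol describes. The same holds for glucose disorders that fall short of type 2 diabetes.

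Section 5.2 counts metabolic syndrome among the principal clinical concerns and says that these concerns shaped the choice of endpoints. A final report that follows section 8 would describe how often metabolic syndrome occurred but not in whom. Section 8.6 repeats all the section 8.5 analyses at 5 years, so the interim report would have the same gap. A SAP author would have to choose between following section 4 and following sections 8.3.2 and 8.5.2.

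**Working it through.** The protocol gives no figure on this point, so there is none to reproduce. The check sets side by side each place that names an outcome to be correlated.

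| Place in protocol | Outcomes named | Related to |
|---|---|---|
| Synopsis and section 4, family objective | Metabolic syndrome, glucose metabolism disorders, malignancy | Familial inheritance |
| Synopsis and section 4, characteristics objective | Metabolic syndrome, glucose metabolism disorders, malignancy | Subject characteristics, medical history |
| Synopsis, secondary endpoints | Type 2 diabetes, malignancy | Blood pressure, BMI, lipids, medical history, family |
| Synopsis, statistical methods | Primary endpoints | Subject characteristics, confounders |
| 5.1 | Type 2 diabetes, malignancy | As in the synopsis endpoints |
| 7.4.1.6 | Type 2 diabetes, malignancy | As in the synopsis endpoints |
| 8.3.2 | Type 2 diabetes, malignancy | As in the synopsis endpoints |
| 8.5.2 | Primary endpoints | Subject characteristics, confounders |
| 8.5.3 | Secondary endpoints | Nothing (descriptive summaries) |

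1. **Is type 2 diabetes a stand-in for the missing outcomes?** Only in part. Section 7.4.1.1 speaks of glucose metabolism disorders other than overt type 2 diabetes. Type 2 diabetes is therefore one such disorder, and there are others. The section also defines metabolic syndrome separately, as insulin resistance plus at least two further criteria.

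2. **What is covered?** The objectives name four outcome components: metabolic syndrome, type 2 diabetes, other glucose disorders and malignancy. Two objectives × four components = 8 pairs. The planned correlations supply type 2 diabetes and malignancy for both objectives, so 2 × 2 = 4 pairs are covered and 8 − 4 = 4 are not. This is a count of pairs, not a measure of their importance.

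3. **Do metabolic syndrome and glucose parameters appear elsewhere as outcomes?** Yes. Section 8.3.2 lists them as secondary endpoints, but as occurrence or change. The correlation endpoint is a separate item in that list and does not refer back to them.

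4. **Can the 8.3.2 factor list simply be applied to metabolic syndrome?** No. In 7.4.1.1, blood pressure, BMI, waist:hip ratio, triglycerides, HDL cholesterol and urinary albumin are components of the definition. Correlating the syndrome with its own components is circular. LDL and total cholesterol are not in the definition.

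**The case against.** The best defence is that the detail belongs to the SAP. Section 8.5.1 leaves detailed analyses, and the minimum data needed to calculate correlations, to that document. Section 8.5.3 promises suitable statistics for all secondary endpoints, with further details to follow. Nothing in the protocol forbids a SAP from adding the missing outcomes. This stands in part. However, what is deferred is method and data sufficiency. The protocol itself names the outcomes to be correlated, consistently, and that list conflicts with its own objectives. A SAP faithful to section 8 would reproduce the gap.

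A second defence is that the consequence is limited: the objectives are secondary, no significance testing is planned, and 5.1 makes the correlations conditional on feasibility. This stands, and it limits the weight of the point.

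Stronger readings are tempting but not supported:

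- A reader might infer that both objectives go wholly unanswered. They do not. Malignancy is named in both objectives and is correlated, and type 2 diabetes covers part of the glucose disorders.
- A reader might infer that the plan correlates only rare outcomes and omits the common one. The protocol gives no expected frequency for any of them, so no event count can be stated. Recorded cases of metabolic syndrome could also be few, because the definition needs several measurements and section 7.4.3 schedules no laboratory tests.
- A reader might infer that the data for the missing analysis are already in hand. Table 1 has fields for them, but its footnote limits collection to what routine care provides.

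**Conclusion.** The point holds as an internal contradiction about which outcomes are to be correlated. Metabolic syndrome, and glucose metabolism disorders other than overt type 2 diabetes, are named in two of the five secondary objectives but appear as outcomes in none of the correlation or association analyses. That part of the two objectives would go unanswered at both the 5-year and the 10-year analysis.

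The conclusion rests on two readings: that type 2 diabetes counts as a glucose metabolism disorder, as 7.4.1.1 implies, and that the statistics listed in 8.5.3 are what is meant there by suitable ones. The SAP is not at hand and may already go further. If it does, the protocol's endpoint wording still needs to be brought into line. The point should be fixed, but it does not threaten the main purpose of the study.

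**What to change.** Choose one of two routes.

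**If the analyses are intended:**
- Add metabolic syndrome, and glucose metabolism disorders other than type 2 diabetes, as outcomes of the correlation endpoint in the synopsis, 5.1, 7.4.1.6 and 8.3.2. All four places need the change, or the protocol stays inconsistent.
- In 8.5.3, add for these outcomes the exploratory association analysis that 8.5.2 gives the primary endpoints, with family history, age, sex and medical history as factors, subject to the minimum data points set in the SAP.
- State that components of the 7.4.1.1 definition (blood pressure, BMI, waist:hip ratio, triglycerides, HDL cholesterol, urinary albumin) are not used as predictors of metabolic syndrome.
- Report the number of evaluable subjects for each association.

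**If they are not intended:** reword the two objectives in the synopsis and section 4 to name type 2 diabetes and malignancy, as the endpoints do.

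The first route costs protocol and SAP wording and one more set of exploratory tables. No new data fields are needed, since Table 1 and section 7.2 already list the items. Because they are recorded only when routine care produces them, the evaluable numbers may be small. The second route costs wording only, but gives up a question the protocol now says it will address.
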